### **Protocol**

We propose to perform a randomized implementation trial to evaluate the efficacy of various implementation methods of the TMW-Newborn educational intervention. The study will be

conducted in temporal proximity to the administration of the universal newborn hearing screen.

After routine delivery, postpartum mothers are admitted to the mother-baby unit for 48-72 hours. At Sacred Heart Hospital, study participation will be offered to every postpartum mother prior to discharge by a hearing screening technician, registered nurse, or registered hospital volunteer during the patient's hospital stay. Study participation will be offered to every mother whose child is receiving the hearing screening at the University of Chicago Medicine and Baptist Hospital-Pensacola. At the University of Chicago Medicine, study participation will be offered by a research assistant or hearing screening technician. At the Baptist Hospital-Pensacola, study participation will be offered by a nurse. The technician, nurse, or registered volunteer will give each mother an electronic tablet with the HIPAA Compliant TMW-Newborn Tech Platform that houses the TMW-Newborn intervention.

The patient experience through the TMW-Newborn intervention within the TMW Tech Platform is as follows:

- Participant selects language (English or Spanish) for viewing videos and completing surveys;
- Participant views Welcome and Consent Video, in which [name] (in English) or another health professional (in Spanish) introduce the study, explain participation, outline risks;
- Participants who agree to participate will then be randomized into one of four conditions:
  - Long TMW-Newborn intervention video without questions interspersed,
  - Long TMW-Newborn intervention video with questions interspersed,
  - Short TMW-Newborn intervention video without questions interspersed, or
  - Short TMW-Newborn intervention video with questions interspersed.
- Participant completes pre-intervention surveys: Baby SPEAK and non-identifying demographics items. These surveys take approximately 10 minutes to complete.
- Participant views TMW-Newborn intervention video, according to her randomized assignment outlined above.
- Participant completes post-intervention surveys: Baby SPEAK, UNHS, and fidelity of implementation.

The hearing screener, nurse, or volunteer will be notified via the TMW Tech Platform to pick up the tablet from the participant upon intervention completion or whenever the participant opts out.

No identifying information is collected within the TMW-Newborn web platform, and the hearing screening technicians will not be able to see or access any of the participants' responses.

This study protocol will only be used at Sacred Heart Hospital, University of Chicago Medical Center, and Baptist Hospital-Pensacola.

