### **Purpose**

The purpose of the proposed research is to perform testing of the Thirty Million Words Initiative Newborn Intervention (TMW-Newborn) with the primary goal of evaluating various implementation methods.

We hypothesize that the TMW-Newborn intervention will:

1. Significantly impact parent knowledge regarding the importance of UNHS follow-up
2. Significantly impact parent knowledge of child development

Additionally, we hypothesize that:

3. The 7-minute version of the video with questions interspersed will most significantly improve parent knowledge of child development
4. There will be no significant differences in effectiveness of the Spanish and English versions of the TMW-Newborn intervention

The hypotheses rely on the existing research data supporting the idea that parental understanding and beliefs will alter parental behavior, and consequently, that increased parental linguistic input will impact their child's cognitive development.

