#### *Randomization*

The hearing screener, nurse, or volunteer will drop off tablets with participants, and only after the participants agree to participate by completing the tablet based consent will they be assigned to one of the four treatment conditions. The TMW-Newborn Web Platform will house the randomization tool that will randomize each participant into one of four treatment groups:

1. Long TMW-Newborn intervention video without questions interspersed,
2. Long TMW-Newborn intervention video with questions interspersed,
3. Short TMW-Newborn intervention video without questions interspersed, or
4. Short TMW-Newborn intervention video with questions interspersed.

There is equal likelihood of each randomization condition occurring.

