#### **Participants**

Participants will include a goal of 10,000 new mothers at Sacred Heart Hospital, University of Chicago Medical Center, and Baptist Hospital-Pensacola. 2,500 will be randomized into each of the four implementation conditions outlined above.

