#### **Analysis**

Paired t-tests will be used to analyze total survey scores before and after intervention. ANOVAs will be used to evaluate differences in outcomes based on SES and other variables in various experimental groups.

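### Hypothesis 4 draws a conclusion about the Spanish and English versions, but mothers choose the language before randomisation, so the comparison is observational and should be stated and analysed as such

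*Combined protocol and SAP*

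**What the plan says.** The Purpose section gives hypothesis 4 as one of two additional hypotheses: "There will be no significant differences in effectiveness of the Spanish and English versions of the TMW-Newborn intervention".

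In the Protocol section, the list of steps on the tablet opens with "Participant selects language (English or Spanish) for viewing videos and completing surveys". The consent video comes next, with a different presenter in each language. Only then: "Participants who agree to participate will then be randomized into one of four conditions".

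The Randomization section says the platform's tool "will randomize each participant into one of four treatment groups". The groups are the long or short video, with or without questions, and "There is equal likelihood of each randomization condition occurring". Language is not a randomised factor, and no stratification by language is stated. All four groups see a TMW-Newborn video.

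Baby SPEAK is taken before and after the video, and demographic items before it. The UNHS survey is listed only after it.

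The Analysis section plans paired t-tests of total scores before and after, and adds: "ANOVAs will be used to evaluate differences in outcomes based on SES and other variables in various experimental groups". It does not name the language comparison, its outcome scale or any adjustment for it. The Participants section says "Participants will include a goal of 10,000 new mothers", 2,500 per condition, and gives no expected share choosing Spanish.

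**The concern.** The hypothesis is worded as a property of the two videos. The design supplies a comparison of two self-selected groups of mothers. Four things change together when a mother chooses Spanish: the video version, the kind of mother in the group, the language in which her knowledge is measured, and the person presenting the consent video. Nothing in the plan separates the first from the other three.

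Nor can each version be judged against a control within its own language group. The earlier trials described under Previous Research enrolled speakers of both languages and had a control video on another topic. This trial has no such arm, so hypothesis 4 rests entirely on comparing the language groups with each other.

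The error could go either way. A less effective Spanish version could look equal if its users start lower and have more room to gain. An equally effective one could look worse on scores after the video. Because the outcome scale is not fixed, the answer could also depend on which score is compared.

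**Working it through.** The plan states no figure for this comparison: no margin, SD, effect size or Spanish share. The only arithmetic to reproduce is 4 × 2,500 = 10,000, which agrees. What follows is illustration on assumed inputs.

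**1. The choice of score matters, and no choice is safe**

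Assume that the versions are identical, that Spanish choosers start g SD lower, and that the within-group pre-post slope is 0.6. Gaps are Spanish minus English, so the starting gap is −g.

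*Model A: the score after the video depends only on the score before it (post = a + 0.6 × pre, same a in both groups).*
- Post gap = −0.6g
- Change gap = −0.6g + g = +0.4g
- Adjusted gap = −0.6g − 0.6 × (−g) = 0

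*Model B: both groups gain the same amount, and the slope is 0.6 because the survey contains measurement error.*
- Post gap = −g
- Change gap = −g + g = 0
- Adjusted gap = −g − 0.6 × (−g) = −0.4g

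| Starting gap g | A: post | A: change | A: adjusted | B: change | B: adjusted |
|---|---|---|---|---|---|
| 0.2 | −0.12 | +0.08 | 0 | 0 | −0.08 |
| 0.5 | −0.30 | +0.20 | 0 | 0 | −0.20 |
| 0.8 | −0.48 | +0.32 | 0 | 0 | −0.32 |

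The true version effect is zero in every row. Under A the adjusted result is right and the change score wrong; under B it is the reverse. The data cannot be relied on to show which model holds, because the groups were not formed by randomisation. In both models the two results differ by (1 − 0.6)g = 0.4g, so reporting both exposes the dependence on the model.

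**2. The sample size does not help**

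Assume SD 1, two-sided alpha 0.05, N = 10,000, no version effect, and a difference b due only to who chose each language.

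SE = √(1/n_S + 1/n_E), and P(significant) = Φ(b/SE − 1.96) + Φ(−b/SE − 1.96).

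Example with 10% Spanish: SE = √(1/1,000 + 1/9,000) = 0.0333. For b = 0.10, b/SE = 3.00 and P = Φ(1.04) = 0.85; the other tail is negligible.

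| Spanish share | b = 0.05 SD | b = 0.10 SD |
|---|---|---|
| 5% | 0.19 | 0.59 |
| 10% | 0.32 | 0.85 |
| 20% | 0.52 | 0.98 |
| 30% | 0.63 | 0.996 |
| 50% | 0.71 | 0.999 |

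At b = 0.20 SD the probability is at least 0.99 throughout. Conversely, a real version effect cancelled by an equal and opposite group difference is declared significant only 5% of the time.

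**3. What adjustment cannot reach**

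No covariate settles whether Baby SPEAK measures alike in the two languages. UNHS knowledge has no score before the video, so neither a change score nor baseline adjustment is available for it.

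**The case against.** The strongest reply is that this is a secondary matter of wording. Hypothesis 4 is an additional hypothesis, and the stated main aim is to compare ways of delivering the intervention. That comparison is randomised and is unaffected, also within each language. Self-selected language is sensible and practically unavoidable, since it could be randomised only among bilingual mothers. In an implementation trial one may also ask simply whether each version works in the mothers who will use it, and then who chooses is part of the question. All of this stands. It supports restating the hypothesis to say so, because its present wording is about the versions.

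A reader might also infer more than the documents support:

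- *That Spanish and English choosers are known to differ.* The Background section ties SES to children's language exposure and to parental knowledge. It says nothing about the SES or starting knowledge of mothers who choose Spanish.
- *That an unadjusted ANOVA by language is planned.* The Analysis section does not name language and does not rule out a model with SES and language together. The analysis is unspecified.
- *That the protocol claims a randomised comparison of languages.* It calls only the four formats randomised.
- *That adjusting for the score before the video removes the bias.* It does so under model A because that model assumes it. Under model B the adjustment creates the bias.

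**Conclusion.** The concern holds in a limited form. As designed, hypothesis 4 is an observational comparison that mixes the version with who chose it and how knowledge was measured, while its wording attributes the result to the version. This follows directly from the order of steps in the Protocol section, the list of randomised conditions and the absence of an arm without the video.

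The size of any bias in this trial is unknown. The spurious gaps of 0.08 to 0.32 SD on the change or adjusted score rest on an assumed slope of 0.6 and assumed starting gaps of 0.2 to 0.8 SD. They show that the result can depend on the choice of score, not that it will. The probabilities of a false difference rest on an assumed group difference and Spanish share.

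The point goes beyond missing detail because it changes what the trial may conclude about the Spanish version. It does not touch the format comparison. Whether a non-significant test could establish similarity without a stated margin is a separate question.

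**What to change.** - Restate hypothesis 4 as an observational comparison of knowledge between mothers who choose Spanish and mothers who choose English, not as an effect of the version.
- For Baby SPEAK, prespecify a model adjusted for the demographic and SES items collected, assigned format and, if recorded, hospital. The sponsor should confirm which SES items are collected and whether hospital is kept in the de-identified data; the documents state neither.
- Report both the change-score result and the result adjusted for the score before the video. Draw a conclusion only where the two agree, and define agreement in advance. Neither is guaranteed unbiased in groups that were not randomised.
- Report the language comparison of UNHS knowledge as descriptive.
- State as a limitation that survey language and consent-video presenter change with the language chosen.

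The cost is a reworded hypothesis and a short addition to the Analysis section, with no change to how mothers choose their language or are randomised. The downside is a narrower claim. Unmeasured differences and survey-language effects remain, and the two analyses may disagree, leaving hypothesis 4 without a conclusion.

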#### **Background**

The Newborn Initiative is both an extension and a focused adaptation of the larger Thirty Million Words initiative. TMW-Newborn is grounded in three main bodies of literature and avenues of research. The first is research on early childhood language acquisition, child development, and child behavior. The foundation of our evidence-based research derives from the differences found in children's language environments, which largely depend on socio-economic status (Hart and Risley 1995). Second is research on maternal health education and health literacy, specifically on prenatal, perinatal and post-natal education. Third is research and data on the Universal Newborn Hearing Screening (UNHS), which occurs during post-partum care. The UNHS is a critical point in time to both deliver the TMW message and to increase follow up for those newborns not passing the initial screening by focusing on the importance of a child's early language environment and the impact of hearing loss on cognitive development.

Our effort therefore lies in bringing these three main bodies of research together to craft a public health intervention, which relies on existing initiatives while adding an important educational component. TMW-Newborn not only aims to impact parents' beliefs about how crucial their role is in creating a stimulating and enriching language environment for their baby, but also seeks to improve rates of re-screening (loss to follow-up) for the universal newborn hearing screening. By emphasizing the importance of talk (and hearing) for cognitive and language development, we seek to encourage families to follow up after the screening if their newborn does not pass.

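### Hypothesis 1 (knowledge of UNHS follow-up) cannot be estimated as planned: the UNHS survey is given only after the video, and every arm watches a TMW-Newborn video

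*Combined protocol and SAP*

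**What the plan says.** The Purpose section gives the trial a "primary goal of evaluating various implementation methods" and then lists four hypotheses. The first is that TMW-Newborn will "Significantly impact parent knowledge regarding the importance of UNHS follow-up". The second is a similar claim about knowledge of child development.

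The Protocol section sets out the measurements around the video. Before it: "Participant completes pre-intervention surveys: Baby SPEAK and non-identifying demographics items". After it: "Participant completes post-intervention surveys: Baby SPEAK, UNHS, and fidelity of implementation".

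Under Randomization, the platform holds a "randomization tool that will randomize each participant into one of four treatment groups". The four groups are the long and short TMW-Newborn videos, each with or without interspersed questions.

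The Analysis section has two sentences: "Paired t-tests will be used to analyze total survey scores before and after intervention" and "ANOVAs will be used to evaluate differences in outcomes based on SES and other variables in various experimental groups". Neither names the UNHS survey or hypothesis 1.

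**The concern.** Hypothesis 1 claims an effect, so it needs a comparison: the same mothers before the video, or similar mothers who did not see it. The plan lists neither for the UNHS survey. Analysis cannot repair this later, because a score from before the video cannot be recovered once a mother has watched it.

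One of the two hypotheses about the intervention's effect would therefore end without an estimate. The subject also matters to the programme. Background says that TMW-Newborn "seeks to improve rates of re-screening (loss to follow-up) for the universal newborn hearing screening", yet no re-screening outcome is listed, and the Consent section says that responses are not linked to identities. Knowledge is not the same as returning for re-screening, but the UNHS survey is the only listed measure that bears on that aim.

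**Working it through.** **1. The plan's own figure.** Participants gives a goal of 10,000 mothers, 2,500 per condition: 4 × 2,500 = 10,000, which agrees. The documents give no alpha, power, effect size, standard deviation or drop-out rate, so the number cannot be derived further. The question here is whether the effect can be estimated at all.

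**2. What is measured, and when (Protocol section).**

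| Survey | Before video | After video |
|---|---|---|
| Baby SPEAK | yes | yes |
| Demographics | yes | no |
| UNHS | no | yes |
| Fidelity of implementation | no | yes |

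Groups without a TMW-Newborn video: 0 of 4.

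**3. Which effect can be formed.**
- Within mothers, the effect is the mean UNHS score after minus the mean before. The second term is missing, so the paired t-test has 0 pairs.
- Between groups, the effect is the mean with TMW-Newborn minus the mean without. Again the second term is missing.
- An ANOVA on the UNHS answers after the video can compare versions or SES groups. It cannot compare any of them with no intervention.
- Hypothesis 2 differs: Baby SPEAK is given at both times, so a change exists, though also without a concurrent control.

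**4. How wide the ignorance is.** Take a yes/no UNHS item with share *p* answering well after the video and an unknown share *b* before it. The change is *p* − *b*. As *b* runs from 0 to 1, the change runs from *p* down to *p* − 1. I borrow *p* = 0.92 from Previous Research, only as an example:
- *b* = 0.50: +42 points
- *b* = 0.80: +12 points
- *b* = 0.92: 0 points
- *b* = 0.95: −3 points
- full range: −8 to +92 points, 100 points wide at any sample size.

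**5. The same item asked at both times.** Let *p01* and *p10* be the shares who move from wrong to right and from right to wrong. With *N* completers,

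Var(change) = [*p01* + *p10* − (*p01* − *p10*)²] / *N* ≤ 1/*N*,

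with the maximum at *p01* = *p10* = 0.5. The 95% half-width is therefore at most 1.96/√*N*:
- *N* = 10,000: 1.96/100 = 1.96 points
- *N* = 5,000: 1.96/70.7 = 2.77 points
- *N* = 2,500 (one arm): 1.96/50 = 3.92 points.

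These are worst cases over every before/after correlation. If the share after the video is fixed at 92%, *p10* is at most 0.08. The variance then peaks at *p01* = 0.58: 0.58 + 0.08 − 0.50² = 0.41. The half-width at *N* = 10,000 is 1.96 × √0.41 / 100, or about 1.3 points. The numbers of completers are assumptions: 10,000 is a goal, and mothers may opt out.

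**6. What the plan can estimate.** UNHS answers after the video can be compared between versions. Assuming two-sided alpha 0.05, 80% power, 2,500 completers per arm and no multiplicity adjustment, the detectable pairwise difference is (1.960 + 0.842) × √(2/2,500) = 0.079 SD. That shows which version does better, provided opt-out does not differ by version. It does not show whether TMW-Newborn changes knowledge.

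**The case against.** **The survey items have not been seen.** If Baby SPEAK contained follow-up items, a paired change could be formed on those items. This stands as a condition. However, nothing in the documents says that it does, and the UNHS survey is listed as a separate instrument.

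**The missing analysis is not peculiar to hypothesis 1.** The Analysis section assigns no test to any hypothesis. That is correct, so the missing assignment is secondary. The core is the absence of a UNHS comparison of either kind.

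**The earlier trials may already supply the evidence.** Previous Research describes a control video and a before/after gain, but the gain is on the Knowledge Survey. The UNHS figure of about 92% is self-reported, given after the video and pooled over all participants. It concerns understanding of the hearing results rather than the importance of follow-up, so it cannot serve as a comparator.

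**Adding a before score still leaves no control.** True. The result would be an uncontrolled change, with the same limit that hypothesis 2 already has. It is weaker than a controlled effect, but it is an estimate where there is now none.

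**The primary goal is to evaluate implementation methods.** This also stands. That goal does not need a UNHS score before the video, which limits how much weight the point carries.

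**Conclusion.** The concern holds. Followed exactly, the plan gives no estimate of the effect in hypothesis 1, and a larger sample does not help. The conclusion rests on the listed schedule, the four listed arms and the assumption that Baby SPEAK does not cover UNHS follow-up. The percentage figures illustrate scale and are not forecasts: they assume a yes/no item, a borrowed 92% and assumed numbers of completers. The point should be fixed, but it ranks no higher than that, because the comparison of video versions and hypotheses 2 to 4 do not depend on a UNHS before score.

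**What to change.** Choose one of two changes.

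**(a) Keep the hypothesis and measure before the video.** In the Protocol section, add UNHS knowledge items to the pre-intervention survey. Use only items that can be answered at that point, not items about the video or the baby's result, since Recruitment has participation offered at the start of the screening. In Analysis, state that the paired analysis also applies to UNHS items asked at both times, and that the mean change is reported with a 95% confidence interval as a before/after change without concurrent control. State the same limit for Baby SPEAK and hypothesis 2.

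*Cost:* a tablet change and a protocol amendment; a pre-survey somewhat longer than the stated 10 minutes or so; possible priming before the video; and perhaps a few new items in English and Spanish if the existing ones refer to the video or the baby's result.

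**(b) Narrow the hypothesis.** Reword hypothesis 1 to say that knowledge of the importance of UNHS follow-up after the video will be described, overall and by version. In Analysis, state that UNHS answers are reported descriptively and compared between versions, with the number who opted out in each.

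*Cost:* a protocol amendment and a smaller claim. The trial would not say whether TMW-Newborn changes this knowledge.

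A variant of (a) is to randomise the timing of the UNHS items, half of the mothers before the video and half after. This gives a concurrent comparison and avoids asking the same mother twice. Under the assumptions used for the version comparison, 5,000 against 5,000 detects 2.802 × √(2/5,000) = 0.056 SD. The cost is that UNHS comparisons between versions drop to 1,250 per arm, or 2.802 × √(2/1,250) = 0.112 SD instead of 0.079. Opt-out during the video would also have to be reported, because it affects only the group asked afterwards.
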